4.2.7 Time to Event Analyses

Pending number of events (as defined below), a time to event analysis may be considered utilising Kaplan-Meier methodology. Kaplan-Meier figures will be presented for the following:

- Time to first VOC event (days) in the defined treatment period: Based on the earliest start date of all VOC events, as collected on the VOC1 eCRF, experienced by a patient during the defined treatment period. Time (days) will be derived as the difference in days from randomisation (Visit 2) to the earliest start date of the VOC events. Patients not experiencing a VOC event will be censored at the end of their defined treatment period, derived as the latest of: Date of EOS visit, date of last available assessment within the defined treatment period or date of premature study discontinuation (regardless of the reason for premature study discontinuation)(refer to Section 3.1.4).
- Time to discontinuation of study treatment (days) (overall and by study treatment related/not study treatment related reason for discontinuation, as defined in [Appendix E Accounting for Missing Data](#)): Patients may prematurely discontinue study treatment administration whilst continuing with scheduled assessments. DOSDISC eCRF collects the variable, *date subject discontinued IP*. Time (days) will be derived as the difference in days from date of first dose of double-blind randomised study treatment to the date of

premature study treatment discontinuation. Patients randomised but not treated will be censored at date of randomisation (Visit 2) = Day 1. Patients completing double-blind randomised study treatment administration will be censored at the date of last dose of double-blind randomised study treatment administration.

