- 2 Partial Dropout Reason-based Multiple Imputation (pDRMI): Missing counts will be imputed differently depending on the reason for dropout; counts for patients in the Ticagrelor groups who dropped out for a study treatment-related reasons are imputed based on the expected VOC event rate in the placebo treatment group, whereas the remaining patients who have dropped out are imputed assuming MAR. Study treatment-related reasons may include (1) AEs, (2) Death and (3) Development of study-specified reasons.
- 3 Dropout Reason-based Multiple Imputation (DRMI): As for pDRMI with study treatment-related reasons and including "severe non-compliance with the protocol".

A review of each patient who withdraws from the study will be carried out prior to database lock and routine study unblinding. The review will include assessment of the reason for

discontinuation of double-blind randomised study treatment for those patients who discontinued the double-blind randomised study treatment and then withdrew from the study and free text for when the reason for withdrawal or discontinuation of double-blind randomised study treatment is “subject decision” or “other”. Based on this review the default assumptions for pDRMI and DRMI may be changed. A list of these patients and the assumptions made under pDRMI and DRMI will be documented prior to database lock and routine study unblinding.

A summary of reasons for patients withdrawing from the study and the corresponding treatment group used to calculate the imputation VOC event rate under MAR, pDRMI, and DRMI is given in [Table 5](#).

Table 5 Reasons for patients withdrawing from the study and the corresponding treatment group used to calculate the imputation VOC event rate under MAR, pDRMI, and DRMI

Reason for withdrawal ^a	MAR	pDRMI	DRMI
Death	Ticagrelor	Placebo	Placebo
Severe non-compliance to protocol	Ticagrelor	Based on review of important protocol deviations prior to study unblinding	Based on review of important protocol deviations prior to study unblinding
Patient lost to follow-up	Ticagrelor	Based on review prior to study unblinding	Based on review prior to study unblinding
Withdrawal by patient	Ticagrelor	Based on review prior to study unblinding	Based on review prior to study unblinding
Other ^b	Ticagrelor	Based on review prior to study unblinding	Based on review prior to study unblinding

^aAll patients withdrawing from placebo have VOC event rate imputed using the placebo treatment group rate.

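### SAP 4.2.7 plans Kaplan-Meier curves for stopping study drug by reason without saying how stops for the other, competing reason are handled

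*SAP*

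**What the plan says.** SAP 4.2.7 makes the analysis optional and dependent on how many events occur; in its words, "a time to event analysis may be considered utilising Kaplan-Meier methodology". Kaplan-Meier is the only method named. One of the two endpoints listed is "Time to discontinuation of study treatment (days) (overall and by study treatment related/not study treatment related reason for discontinuation").

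The event date is the single recorded date on which the patient discontinued study drug. There are two censoring rules. A child who never received study drug is censored on Day 1. For those who finish treatment, the rule is: "Patients completing double-blind randomised study treatment administration will be censored at the date of last dose of double-blind randomised study treatment administration".

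Neither rule covers a patient who stops for the reason that is not being plotted. For the related/not-related split the section points to Appendix E, which says: "Study treatment-related reasons may include (1) AEs, (2) Death and (3) Development of study-specified reasons". The DRMI variant adds severe non-compliance, and reasons are reviewed before unblinding. Neither document mentions competing risks or cumulative incidence.

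**The concern.** Each patient has at most one date of permanent discontinuation and one class of reason. Stopping for either class ends treatment and rules out stopping for the other, so these are competing events.

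A by-reason Kaplan-Meier curve needs a rule for stops of the other class. The usual choice is to censor them. Censoring takes those children out of the risk set and assumes they would have had the same later hazard of the plotted reason as children still on drug. They are already off drug, so that hazard is hypothetical for them. If 1-KM is then read as the proportion who stop for that reason, it is too high, and the two reason curves together exceed the overall curve.

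What is at stake is a descriptive view of tolerability. Appendix E says the efficacy estimand should be read alongside why and when patients come off treatment, and these figures are where timing by reason would be seen. The excess also depends on how much stopping for the other reason occurs in each arm, so it need not be the same in both.

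**Working it through.** **Inputs.** SAP 4.2.7 states no numerical result, so there is no figure to reproduce. The only attrition figure is the increase from 154 to 182 patients for dropout (Protocol 8.2, SAP 1.3). It corresponds to 1 - 154/182 = 15.4%; equivalently, 154/0.85 = 181.2, rounded up to 182. That is dropout from the study, not stopping of study drug, and serves here only as a reference point. Total stopping F and the share s due to the plotted reason are assumed.

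**Formulas.** With proportional cause-specific hazards and cumulative total hazard L = -ln(1 - F):

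- cumulative incidence for the reason = s × (1 - exp(-L)) = s × F
- 1-KM with other-reason stops censored = 1 - exp(-s × L) = 1 - (1 - F)^s

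Example with F = 0.30 and s = 0.5: cumulative incidence = 0.5 × 0.30 = 15.0%; 1-KM = 1 - 0.70^0.5 = 16.3%.

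| Total stopping F | Share s | Cumulative incidence | 1-KM | Excess (points) | Relative excess | Sum of both reason curves |
|---|---|---|---|---|---|---|
| 10% | 0.50 | 5.0% | 5.1% | 0.1 | 2.6% | 10.3% |
| 15.4% | 0.50 | 7.7% | 8.0% | 0.3 | 4.2% | 16.0% |
| 30% | 0.50 | 15.0% | 16.3% | 1.3 | 8.9% | 32.7% |
| 30% | 0.25 | 7.5% | 8.5% | 1.0 | 13.7% | 32.0% |
| 50% | 0.50 | 25.0% | 29.3% | 4.3 | 17.2% | 58.6% |
| 50% | 0.25 | 12.5% | 15.9% | 3.4 | 27.3% | 56.5% |

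The sum of the two reason curves should equal F and exceeds it in every row.

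**Check by simulation.** 400,000 patients, constant hazards, equal split, follow-up uniform on 12 to 24 months, read at 23.4 months:

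| Total stopping by 24 months | True value | Kaplan-Meier, other reason censored | Aalen-Johansen | Kaplan-Meier, other-reason stops kept at risk to administrative end |
|---|---|---|---|---|
| 15.4% | 7.5% | 7.8% | 7.5% | 7.5% |
| 30% | 14.7% | 16.0% | 14.7% | 14.7% |
| 50% | 24.6% | 28.7% | 24.5% | 24.5% |

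The last column shows that the bias comes from censoring the other reason. A different, unstated rule would remove it.

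**Comparison between arms.** Suppose 10% in each arm truly stop for a related reason, but unrelated stopping is 10% in one arm and 30% in the other.

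- First arm: F = 20%, s = 0.5, so 1-KM = 1 - 0.80^0.5 = 10.6%.
- Second arm: F = 40%, s = 0.25, so 1-KM = 1 - 0.60^0.25 = 12.0%.

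The curves would differ although the proportions stopping for a related reason are equal.

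**The case against.** The strongest reply is that the fault is inferred. SAP 4.2.7 does not say that other-reason stops are censored. If they were kept in the risk set to their administrative end date, the curve would estimate the right proportion, as the simulation shows. This is feasible, because patients who stop study drug are asked to stay in follow-up. That stands: a reader might infer from the SAP that each curve is bound to overstate, but the text supports only the conditional statement. A reader might equally suppose that each curve would be restricted to patients who stopped for that reason, and so reach 100% by construction; nothing in the SAP says so.

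Second, crude percentages by reason are already planned: in the disposition summary (SAP 4.2.1), in the adverse event summary for stops due to adverse events (SAP 4.2.9.1), and in the tables of reasons for discontinuation by randomised group (Appendix E). These are not inflated by the censoring described here. This stands, and it limits the harm. The tables do not show timing, however, which is the purpose of the figure.

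Third, a Kaplan-Meier curve by cause can be defended as a net quantity. If the cause-specific hazards are equal in both arms and the causes are independent, those curves agree between arms, while cumulative incidence differs wherever other-reason stopping differs. This is correct. The bias exists only when the curve is read as the proportion who stop for that reason. The SAP does not prescribe that reading, though it is the natural one for a figure of discontinuation by reason.

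Fourth, no test, hazard ratio or decision rule is attached, and time to discontinuation is not an outcome measure for any listed objective. A reader might infer that a tolerability conclusion or the arm comparison in this trial is compromised; the documents do not support that.

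**Conclusion.** The point holds as a low-cost improvement of low materiality. The plan names an estimator for by-reason discontinuation that, in its usual implementation, does not estimate the proportion stopping for each reason, and it gives no rule that would avoid this.

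The size rests on assumptions: proportional cause-specific hazards, other-reason stops censored, and assumed values for total stopping and its split. Across total stopping of 10% to 50% and shares of 25% to 75%, the excess runs from 0.1 to 4.3 points, or about 1% to 27% relative. The top of the relative range needs half of all patients to stop and only a quarter of those to stop for the plotted reason, and nothing in the documents points to that. At a level equal to the study-dropout allowance, with an equal split, the excess is about 0.3 points.

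The overall discontinuation curve, the primary analysis, and the planned secondary and safety analyses are unaffected.

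**What to change.** In SAP 4.2.7, keep Kaplan-Meier for overall time to discontinuation. For the by-reason figures, specify Aalen-Johansen cumulative incidence by treatment group, with the other class of reason as a competing event and the existing censoring of untreated and completing patients unchanged. The two reason curves will then add to one minus the overall Kaplan-Meier curve.

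Two definitions should be settled in the same edit, because both determine which class a stop falls in:

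- whether the pDRMI or the DRMI list in Appendix E defines a related reason, since they differ on severe non-compliance;
- whether patients taken off drug by the sponsor's early termination (SAP 3.1.4.1) count as completers, and so are censored, or as not-related stops.

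The cost is a few sentences of SAP text and a different estimator for one optional figure. Dates and reasons are already collected, and the reasons are already reviewed before unblinding.

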4.2.8 Secondary Efficacy Variables

In general, and unless otherwise specified, the secondary efficacy analyses will be performed using the FAS (refer to Section 2.1) by planned treatment group. Palatability and swallowability will be performed using the safety analysis set by actual double-blind randomised study treatment received.

4.2.8.1 Number of Painful Crises

Descriptive statistics will be presented for the number of painful crises experienced by a patient over the treatment period by planned treatment group using the FAS. Descriptive statistics will also be presented for the number of individual painful crises irrespective of the number of days between the onset of painful crises.

The number of painful crises will be analysed using the negative binomial regression model, as described in Section 4.2.6.1 for the primary endpoint. Similarly, as sensitivity analysis, the same negative binomial regression model will be used on the number of individual painful crises irrespective of the number of days between the onset of painful crises.

4.2.8.2 Number of ACSs

Descriptive statistics will be presented for the number of ACSs experienced by a patient over the defined treatment period by planned treatment group. Descriptive statistics will also be presented for the number of individual ACSs irrespective of the number of days between the onset of ACSs.

If numbers allow, the number of ACSs will be analysed using the negative binomial regression model as described in Section 4.2.6.1 for the primary endpoint. Similarly, as sensitivity analysis, the same negative binomial regression model will be used on the number of individual ACSs irrespective of the number of days between the onset of ACSs.

4.2.8.3 Duration of Painful Crises

Descriptive statistics will be presented for the total duration (days) (taking into account overlapping painful crisis days + 7-day onset rule) of painful crises experienced by a patient over the defined treatment period by planned treatment group. Patients who do not experience any painful crisis will have their duration of painful crises set to 0.

If numbers allow, the total duration (days) (taking into account overlapping painful crisis days + 7-day onset rule) of painful crises will be analysed using the negative binomial regression model, as described in Section 4.2.6.1.

4.2.8.4 Number of VOC Events Requiring Hospitalisation or Emergency Department Visits

Descriptive statistics will be presented for the number of VOC events requiring hospitalisation or emergency department visits experienced by a patient over the treatment period by planned treatment group.

If numbers allow, the number of VOC events requiring hospitalisation or emergency department visits will be analysed using the negative binomial regression model, as described in Section [4.2.6.1](#).

4.2.8.5 Number of Days Hospitalised for VOC Events

Descriptive statistics will be presented for the total number of days hospitalised (taking into account potential overlapping hospitalisation days of VOC components) for VOC events experienced by a patient over the defined treatment period by planned treatment group. Patients who do not experience any VOC event as well as patients who do not experience any VOC events requiring hospitalisation due to VOC will have their number of days hospitalised for VOC set to 0.

If numbers allow, the total number of days hospitalised for VOCs (taking into account potential overlapping hospitalisation days of VOC components) will be analysed using the negative binomial regression model, as described in Section [4.2.6.1](#).

4.2.8.6 Number of Acute SCD Complications

Descriptive statistics will be presented for the number of acute SCD complications experienced by a patient over the treatment period by planned treatment group.

If numbers allow, the number of acute SCD complications will be analysed using the negative binomial regression model, as described in Section [4.2.6.1](#).

If reported by at least 10 patients in total across the two treatment groups, the individual events comprising acute SCD complications will be assessed descriptively as exploratory endpoints (TIA/ischaemic stroke, hepatic sequestration, splenic sequestration, priapism, and dactylitis).

4.2.8.7 Number of Days Hospitalised for Acute SCD Complications

Descriptive statistics will be presented for the total number of days hospitalised (taking into account potential overlapping hospitalisation days) for acute SCD complications experienced by a patient over the defined treatment period by planned treatment group. Patients who do not experience any acute SCD complication as well as patients who do not experience any acute SCD complications requiring hospitalisation will have their number of days hospitalised for SCD complications set to 0.

If numbers allow, the total number of days hospitalised (taking into account potential overlapping hospitalisation days) for acute SCD complications will be analysed using the negative binomial regression model as described in Section 4.2.6.1.

4.2.8.8 Number of Sickle Cell-related Red Blood Cell Transfusions

Descriptive statistics, including arithmetic mean, SD, median, min and max, will be presented for the number of sickle cell-related red blood cell transfusions received by a patient over the defined treatment period by planned treatment group.

If numbers allow, the number of sickle cell-related red blood cell transfusions will be analysed using the negative binomial regression model as described in Section 4.2.6.1.

4.2.8.9 Health-related Quality of Life (HRQL) and Fatigue

Descriptive statistics will be presented for patients in FAS, by planned treatment group and visit, for the PedsQL SCD Module considering the 9 sub-scales (refer to Section 3.3.6.1 for details) and the derived total score as well as the change from baseline in these scores to each post-baseline visit, based on scheduled eCRF visit (number and name).

Similarly, for the Multidimensional Fatigue Scale considering the 3 sub-scales (refer Section 3.3.6.2 for details) and the derived total score as well as the change from baseline in these scores to each post-baseline visit, based on scheduled eCRF visit (number and name)..

All descriptive statistics will be presented by age-specific category only. Individual patient data will be listed. It should be noted that child self-reported or caregiver-reported cannot be ascertained from the data collected and as such is not presented in relevant tables and listings.

4.2.8.10 Days Absent from School/Work Due to SCD

Descriptive statistics will be presented for the proportion of days absent from school/work due to SCD by planned treatment group, only for those patients who were going to school or work at randomisation (Visit 2).

4.2.8.11 Intensity of Pain During VOC Events and Number of VOC Events by Age Group

The number (n) and percentage (%) of patients experiencing at least one individual VOC event will be calculated based on FAS and will be presented by age group (<5 years and ≥ 5 years) and planned treatment group. Similarly, the total number of individual VOCs will be presented by age group (<5 years and ≥ 5 years) and planned treatment group.

Descriptive statistics of the average intensity of pain during VOCs will be presented by age group (<5 years by means of FLACC and for patients ≥ 5 years by means of FPS-R).

4.2.8.12 Type of Analgesics Used During VOC Events

Analgesics use during VOC events as well as the type of analgesics (opioid/non-opioid) will be summarised and presented, by planned treatment group, on both event and patient level:

- Number of (individual) VOC events occurring during the defined treatment period
- Analgesics use (during individual VOC events)
- Type of analgesics:
 - Opioid
 - Non-opioid

At event level, only the number of observations (n) in each category will be presented.

At patient level, the percentage (%) of patients reporting at least one VOC event will be calculated based on FAS. Percentage of analgesics use will be calculated based on the total number of patients in FAS with at least one VOC event reported in the defined treatment period. Patients with multiple analgesics used during VOC events will be counted only once in that category. Patients who used both types of analgesics (opioid/non-opioid) will be counted once in both categories.

4.2.8.13 Swallowability and Palatability Data

Swallowability and palatability data will be summarised taking into consideration the administration formulation. A summary table will be produced showing the number (n) and percentage (%) of patients with ease/difficulty of swallow based on the categories defined in Section [3.3.10](#).

In addition, the number (n) and percentage (%) of patients with a negative response to palatability will be presented. Percentage will be based on the total number of patients in the safety analysis set, per age group as determined at randomisation (Visit 2), who completed the correct age-specific assessment for study treatment palatability per formulation, by actual treatment group. Number of patients reporting a negative response will be also presented based on the categories defined in Section [3.3.10](#).

4.2.9 Safety

Safety summaries will be presented using the safety analysis set (refer to Section [2.1](#)), unless otherwise specified, by actual study treatment received. No formal statistical analyses will be performed on safety data.

4.2.9.1 Adverse Events

Summary tables will include on-treatment/off-treatment AEs (refer to Section [3.4.1](#)) only, unless otherwise specified. That is, pre-treatment AEs will be included in the patient data listings only.

Separate overall summary tables will be produced for AEs on-treatment and off-treatment showing the number (n) and percentage (%) of patients with at least one AE in each of the following AE categories: Any AE, any AE causally related to study treatment, maximum AE intensity, any AE with an outcome of death, any SAE and discontinuation of study treatment due to AEs. The overall summary tables will be repeated by age group as follows:

- ≥ 2 years to <12 years at randomisation (Visit 2)
- ≥ 12 years to <18 years at randomisation (Visit 2)

AEs/SAEs will be summarised by MedDRA SOC and MedDRA PT by actual study treatment received and by the same age group as previously defined. Events will be sorted by international order for system organ class (SOC) and alphabetically for PTs within each SOC. For each SOC/PT, the number (n) and percentage (%) of patients reporting at least one event at each level of summarisation (SOC/PT) will be presented ie, for a patient with multiple occurrences of the same AE, the event will only be counted once per PT/SOC. Patients with events in more than one SOC/PT are counted once per individual SOC/PT.

Most common AEs will be summarised separately by MedDRA PT, where most common is defined as a frequency $> 5\%$ in either of the two treatment groups and sorted by decreasing frequency based on the ticagrelor treatment group. Similarly, for presentation of non-serious AEs. In addition, AEs will be summarised by MedDRA PT and causality/relatedness. If a patient reports multiple occurrences of the same AE, the patient will be summarised only for the most related. Similarly, by MedDRA PT and maximum reported intensity. If a patient reports multiple occurrences of the same AE, the patient will be summarised only for the maximum reported intensity. In case of missing causality/relatedness and/or intensity, a missing category will be presented per relevant PT.

The event rate per 100 patient years will be presented by treatment group, where:

Event rate per 100 patient years = (number of patients with AEs/total exposure years) \times 100 (refer to Section 4.2.5).

Where:

Year = 360 days.

Patient data listings of AEs leading to death, SAEs, SAEs causally related to study treatment and discontinuation of study treatment due to AEs will be presented. In addition, COVID-19 suspected AEs/SAEs and COVID-19 confirmed AEs/SAEs will be presented in a separate patient data listing. Dose level at onset of AEs/SAEs will also be presented in patient data listings.

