8.2 Sample size estimate

The number of VOCs is assumed to have a negative binomial distribution with shape parameter 0.8. The mean number of crises per year is assumed to be 2.0 in the placebo group with reduction of 50% in the ticagrelor group. Patients will be randomised to 1:1 ratio and with minimum follow-up of 12 months and average follow-up of 18 months, 154 patients provide about 90% power for a 2-sided test of the mean number of crises for ticagrelor versus placebo, at significance level 5%. Allowing for dropouts, the sample size is increased to 182. The calculations were based on simulation with 5,000 repetitions.

Scenarios and simulations were evaluated to assess the risk with shorter and longer mean follow-up time. To ensure that the study is adequately powered the recruitment rate will be monitored and the sample size may be adjusted to a maximum of 200 patients. With a mean follow-up time of 13 month, 200 patients will provide 90% power to detect a reduction of 50% in the ticagrelor group.

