3.1.5 Safety Follow-up Period

The safety follow-up period follows the treatment period with the final visit, per schedule of assessments, up to a maximum of 19 days after the EOS visit.

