3.1.7.2 Off-treatment Period

The off-treatment period follows the end of the on-treatment period, 1 day after the “last dose of study treatment + 7 days” as defined in Section 3.1.7.1.

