4.2.9.3 Bleeding Events

For the safety analysis set, summary tables will include on-treatment/off-treatment bleeding events (refer to Sections 3.4.4) only. Pre-treatment bleeding events will be included in the patient data listings only. Any bleeding events occurring after premature study treatment discontinuation regardless of initiation of alternative therapy for SCD will be flagged in the patient data listings.

Total number of bleeding events (n only), frequency (n and %) of patients who have experienced at least one bleeding event on-treatment/off-treatment will be presented by actual study treatment received. Percentage of patients experiencing at least one bleeding event will be based on the safety analysis set, by actual treatment group.

Event-level and patient-level summary of bleeding characteristics: Severity of bleed, nature of the bleed and primary location of the bleed will also be presented. Percentage of bleeding events reported in each category will be based on the total number of bleeding events experienced by patients in the safety analysis set. Percentage of patients in each category will be based on the total number of patients in the safety analysis set who experienced at least one bleeding event, by actual treatment group.

All bleeding events at any time during the study will be presented in patient data listings. Dose level at onset of the bleeding event will also be presented.

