4.2.9.4 Blood Product Transfusions

For the safety analysis set, summary tables will include on-treatment/off-treatment blood product transfusions (refer to Sections 3.1.7.1 and 3.1.7.2), unless otherwise specified. Transfusions (as defined in Section 3.4.6) including the number of patients who have had any AE leading to the need for a transfusion, the number of transfusions for each patient, and the number of units transfused along with the type of blood product transfused will be presented by actual study treatment received.

All blood product transfusions at any time during the study will be presented in patient data listings. Dose level at onset of the blood product transfusion will also be presented.

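### Off-treatment adverse event and bleeding tables use the whole safety set as denominator and ignore very unequal off-treatment observation time, so they can mislead if early stopping differs between arms

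*SAP*

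**What the plan says.** SAP 3.1.7.1 ends the on-treatment period 7 days after the last dose. SAP 3.1.7.2 continues: "The off-treatment period follows the end of the on-treatment period, 1 day after the" last dose plus 7 days. It gives no upper limit, and neither does the off-treatment category in SAP 3.4.1. Observation ends with the safety follow-up visit, which SAP 3.1.5 places "up to a maximum of 19 days after the EOS visit". Protocol Table 2 schedules that visit 14 ± 5 days after EOS.

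Protocol 3.9.2 and 3.9.3 keep patients who stop study drug in follow-up and ask them to attend regular visits.

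For adverse events, SAP 4.2.9.1 plans: "Separate overall summary tables will be produced for AEs on-treatment and off-treatment showing the number (n) and percentage (%) of patients". SAP 4.1.1 makes the analysis set the default denominator. For bleeding, SAP 4.2.9.3 says so directly: "Percentage of patients experiencing at least one bleeding event will be based on the safety analysis set, by actual treatment group". For transfusions, SAP 4.2.9.4 says only that "summary tables will include on-treatment/off-treatment blood product transfusions". It lists numbers of patients, transfusions and units, so a percentage there would follow only from the general rule in 4.1.1.

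The rate per 100 patient-years in SAP 4.2.9.1 divides patients with events by total exposure years. SAP 4.2.5.1 counts those years from first to last dose. The SAP defines no off-treatment person-time.

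**The concern.** A percentage of patients with an event compares arms fairly only if the arms were watched for similar lengths of time. Off treatment, the time watched depends almost wholly on whether a patient stopped early.

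Early stopping may be linked to treatment. Protocol 3.9.1 lists major bleeding and repeated minor bleeding among the situations for permanent discontinuation, and Protocol 1.3 says antiplatelet agents raise bleeding risk. If stopping were more common on ticagrelor, its off-treatment percentages would rise through longer observation alone. A reader could take that for carry-over or rebound. Conversely, a real early signal after stopping could be diluted by late events from long-followed stoppers. Safety is a stated comparative objective (Protocol 2.3) and is not formally tested, so readers will judge it from these tables.

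**Working it through.** **1. The plan's own figure.** Protocol 8.2 states: "154 patients provide about 90% power for a 2-sided test of the mean number of crises for ticagrelor versus placebo, at significance level 5"%. It assumes a "negative binomial distribution with shape parameter 0.8" and adds: "The mean number of crises per year is assumed to be 2.0 in the placebo group with reduction of 50"%. Mean follow-up is 18 months. With dispersion 1/0.8 = 1.25 and 77 per arm, the variance of the log rate ratio is (1/3 + 1.25 + 1/1.5 + 1.25)/77 = 0.0455, so SE = 0.213. Then ln 2/0.213 = 3.25, and Φ(3.25 − 1.96) = 90.2%. The stated power is reproduced. With dropouts the plan randomises 182, or 91 per arm. The 2.0 rate is a usable adverse event rate below, because Protocol 6.3.9 has each VOC recorded as an adverse event.

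**2. Off-treatment window for a patient dosed until EOS.** Visit day minus 7: 14 − 7 = 7 days, range 9 − 7 = 2 to 19 − 7 = 12. SAP 3.1.4.1 has ongoing patients stop drug at the common study end date, and Protocol 4.2.3 allows the EOS visit up to 30 days after that date. The window could then be 30 + 14 − 7 = 37 days, at most 30 + 19 − 7 = 42. The two sections leave open which applies.

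**3. Expected percentage at equal risk.** Let s be the share stopping early, h the event rate per year (the same in both arms), and c and e the off-treatment days for completers and stoppers, with a 360-day year as in the SAP:

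% = 100 × [(1 − s)(1 − exp(−h·c/360)) + s(1 − exp(−h·e/360))]

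The values of s, e and the bleeding rate are assumptions, as the documents give none. For h = 2, c = 7, e = 270, the bracketed probabilities are 0.0381 and 0.7769. At s = 10%: 0.9 × 0.0381 + 0.1 × 0.7769 = 11.2%. At s = 20%: 0.8 × 0.0381 + 0.2 × 0.7769 = 18.6%.

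| Events/year | c / e (days) | 10% stop | 20% stop | Ratio |
|---|---|---|---|---|
| 2 | 7 / 270 | 11.2% | 18.6% | 1.66 |
| 2 | 7 / 90 | 7.4% | 10.9% | 1.48 |
| 2 | 37 / 270 | 24.5% | 30.4% | 1.24 |
| 2 | 37 / 90 | 20.7% | 22.7% | 1.10 |
| 0.2 (assumed bleeding) | 7 / 270 | 1.7% | 3.1% | 1.78 |

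**4. Stopping as a rate over time.** These are simulated ratios with exponential stopping at 10% versus 20% per year and equal event rates of 0.3, 1 and 3 per year:

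| Follow-up, completer window, retention | Ratios |
|---|---|
| 12–24 months, 7 days, all stay | 1.75, 1.70, 1.57 |
| 12–24 months, 37 days, all stay | 1.43, 1.35, 1.21 |
| 6–24 months, 7 days, all stay | 1.71, 1.65, 1.53 |
| 3–24 months, 37 days, half of stoppers leave | 1.21, 1.16, 1.09 |
| 12–24 months, 7 days, all stay, stopping 15% vs 20% | 1.26, 1.25, 1.21 |

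Stoppers who leave are given the completer window. In the first row, stoppers average about 300 off-treatment days. With equal stopping the ratio is 1.0.

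**5. The SAP's existing rate does not help.** Take the first row of step 3 and 540 days of total follow-up. Mean dosing exposure is (0.9 × 540 + 0.1 × 270)/360 = 1.425 years versus (0.8 × 540 + 0.2 × 270)/360 = 1.35 years. Then 11.2/1.425 = 7.9 and 18.6/1.35 = 13.8 per 100, a ratio of 1.75.

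**6. Off-treatment person-time.** For the same row with 91 per arm, off-treatment years are 91 × 33.3/360 = 8.4 and 91 × 59.6/360 = 15.1, with 16.8 and 30.1 expected events. Both arms then give 200 per 100 off-treatment patient-years.

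**7. Limit of a pooled rate.** Suppose both arms have the same early peak: 6 events per year in the first 7 off-treatment days, then 1 per year. In the set-up of the first row of step 4, the pooled rates are 174 versus 142 per 100 patient-years, a ratio of 0.82 that wrongly favours the arm with more stopping. Over those 7 days alone, both arms show 6 per year.

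**The case against.** A reader might infer that ticagrelor is bound to show more off-treatment events. The documents do not support that. They give no stopping rates, and Protocol 1.1 and 1.3 report no bleeding during treatment in HESTIA1, a frequency similar to placebo in HESTIA2, and no indication of increased bleeding risk. The effect needs differential stopping. Even then it holds only in expectation at equal risk, so chance or a true difference can offset it.

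The sizes also depend on the trial as run. The SAP was revised for early termination, so 12 months is no longer a guaranteed minimum, and some stoppers will leave follow-up altogether. The completer window may be over five weeks rather than one. These points stand. They bring the ratio down to about 1.1 to 1.4 in the less favourable cases but do not remove it.

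A reader might also infer that the transfusion tables are explicitly planned as percentages of the safety set. SAP 4.2.9.4 does not say so, although raw counts carry the same imbalance.

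Other planned outputs give context: disposition with reasons and study day of discontinuation (SAP 4.2.1), exposure (4.2.5), possible Kaplan-Meier curves of time to treatment discontinuation (4.2.7), and flags in the bleeding listings (4.2.9.3). They let a careful reader see differential stopping but do not adjust the off-treatment tables for it. SAP 4.2.9 plans no formal safety analysis, so the harm is confined to how the tables are read.

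**Conclusion.** The concern holds in a limited form. Off-treatment percentages for adverse events and bleeding, and any percentages for transfusions, pool patients watched for about 1 to 6 weeks with patients who may be watched for many months. Nothing in the SAP corrects for this. If stopping differs between arms, the arm with more stopping is expected to look worse off treatment at equal risk. The ratio is about 1.1 to 1.75 for assumed stopping of 10% versus 20% per year, about 1.2 to 1.3 for 15% versus 20% with 12–24 months of follow-up and a 7-day completer window, and 1.0 for equal stopping. All stopping and event rates other than the 2.0 VOC rate are assumptions. The on-treatment tables and the primary test are not touched. This is a cheap improvement to descriptive reporting, not a flaw in the trial's main conclusion.

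**What to change.** In SAP 4.2.9.1, 4.2.9.3 and 4.2.9.4:

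- Derive off-treatment time for each patient as last dose + 8 days to last contact.
- Beside n and %, show off-treatment patient-years per arm and events per 100 off-treatment patient-years.
- Also show events within a fixed window after the last dose that completers cover too, for example up to the safety follow-up visit, among patients observed in that window. This compares early carry-over or rebound over like time, which step 7 shows a pooled rate cannot do alone.
- State how the EOS visit relates to the common study end date, so that the completer window is known.

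Limiting the denominator to patients with at least one off-treatment day would not be enough, since almost everyone who attends the safety visit qualifies.

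The cost is one derived variable from dates already collected and a few added columns. The rates will be imprecise because off-treatment time is short, so the patient-years should be printed next to them.
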